**8.6 TRIAL CLOSURE**

The minimum number of children to be recruited into each arm is 36, however, as this is a proof of concept study, an accurate power calculation cannot be performed, indeed part of the reason for this study is to determine the size of a larger trial that would be needed to definitively answer whether pathological phenotype based management is superior to current clinical guidelines. Therefore, recruitment of patients will continue until the end of the trial funding period, December 2018.

## **9.0 STATISTICS AND DATA ANALYSIS**

Categorical data will be presented as number and percentage and comparisons between groups done using the chi squared or Fishers exact test. All numerical data will be tested for normality and normally distributed data will be presented as mean  $\pm$  SD and comparisons between groups done using the 2 sample independent t test. For the data that are not normally distributed the median (IQR) will be presented and comparisons between groups done using the Mann-Whitney test. Poisson regression will be done to determine the factors that affect the primary endpoint, the number of unplanned hospital visits.

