### **Number of subjects:**

Based on published data for children with moderate preschool wheeze it is apparent that approximately five healthcare attendances occur per child per year. In the current study, we wish to reduce the proportion of healthcare contacts by at least one-third per year. In order to achieve this with 80% power, and accepting statistical significance at the 5% level, we require a minimum of 36 evaluable patients with moderate wheeze per group. Evaluable patients are those from whom at least a blood sample to assess inflammation and an oropharyngeal swab to determine infection can be obtained prior to randomisation.

A total of at least 72 children will therefore be recruited. However, this is the minimum number, and we aim to recruit 100 children (50 per group) if possible.

The number of subjects is not based on a precise power calculation as this is a proof of concept study to determine the feasibility of this approach, and to inform a future power calculation for a large multi-centre trial addressing the same question.

**3.1 Study Outcome Measures:** Primary outcome – number of unscheduled healthcare visits in the 4 month intervention period. Secondary outcomes – health related quality of life for the child and family, number of hospitalisations, days of oral steroids.

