##### **4.1 Pre-randomisation Evaluations**

All participants will undergo an initial research / screening visit which will involve the following tests:

Full blood count and Vitamin D

Total serum IgE and RASTs to house dust mite, grass pollen, tree pollen, cat, dog, aspergillus, milk, egg, peanut

Assessment of lung function by incentive spirometry and lung clearance index (LCI) using the multiple breath washout technique  
Exhaled nitric oxide – using the offline tidal breathing technique  
Sputum induction using nebulised hypertonic saline  
Oro-pharyngeal swab  
Symptom questionnaire  
Health related quality of life questionnaire  
[Urine sample for cotinine levels \(and for storage if parents consent\)/salivary cotinine](#)

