**The baseline assessments to be made at the research visit include:**

**Symptom questionnaire**

Parents of all patients will complete a written questionnaire to obtain details of symptom duration, onset and severity, including history of medications, allergies, family history. All parents will also be shown a validated video questionnaire to obtain objective confirmation of wheeze(31). Health related quality of life (HRQOL) for the child and family will be determined using the validated Child Health Questionnaire(32-34).

**Sample collection** – all parents will be asked for consent for the child to undertake FeNO measurement, have a blood sample taken, undergo sputum induction and have an oropharyngeal swab taken.

**1.** **Blood** will be taken for a peripheral eosinophil count, total IgE and specific IgE to common aero and food allergens.

**2.** **Sputum** induction will be performed using nebulised hypertonic saline (3.5%), chest physiotherapy and oropharyngeal suction using previously described techniques for preschool children. We have now established a protocol for sputum induction in preschool children with various airways diseases, including wheezing, and have shown the procedure can be performed safely and with up to 95% success. Sputum will be processed for bacterial culture and cytology.

**3.** **Lung function** will be performed using the multiple breath washout technique to obtain a measurement of lung clearance index (LCI) as previously described, and according to recent American Thoracic Society recommendations. This technique does not require voluntary manoeuvres and needs minimal patient cooperation and is therefore suited to preschool children. We have recently performed a pilot feasibility study in preschool children attending the outpatient clinic, and demonstrated only 27% were able to perform LCI, but if the index was reduced to gas clearance in half the time (LCI0.5), the success rate increased to 77%. Importantly, it has been shown that LCI measurements can be reliably shortened in children to improve the feasibility of obtaining data. We will therefore perform LCI and LCI0.5 in this study, and will be able to use the data for more formal assessments of feasibility in preschool children with wheeze. This has not been reported to date. Incentive spirometry using computer aided incentive devices will also be performed, but the success of this is anticipated to be lower than that for LCI.

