**Immediate follow-up assessment:**

After the 4 month intervention period, all children will be asked to return for a follow-up visit during which the following assessments will be made:

**Symptoms** – using symptom questionnaire

**Health related quality of life** questionnaire

Number of unscheduled healthcare visits in the 4 month period (these will also have been recorded during the weekly telephone calls)

**Lung function** assessment (using multiple breath wash-out technique as described in Section 8.2 above)

**Exhaled nitric oxide** measurement (using the offline tidal breathing technique as described in Section 8.2 above)

**Sputum induction** – to assess inflammation and infection

Urine- for storage if parents consent

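### Section 9.0 makes no use of the baseline quality-of-life score when comparing the arms, which costs precision that a baseline-adjusted regression would recover

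*Combined protocol and SAP*

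**What the plan says.** Section 9.0 is the whole analysis plan. Numerical data are tested for normality. If normal, they are summarised by mean and SD, with "comparisons between groups done using the 2 sample independent t test". If not, they are summarised by median and IQR, with "comparisons between groups done using the Mann-Whitney test". The one model is for the primary count: "Poisson regression will be done to determine the factors that affect the primary endpoint, the number of unplanned hospital visits". Its covariates are not listed. Baseline adjustment, change from baseline, and adjustment for the stratification factors of Section 5.1 (sex and age) are not mentioned anywhere.

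Section 3.1 lists among the secondary outcomes "health related quality of life for the child and family", and the hypothesis in Section 1.2 names it. Section 4.1 includes a "Health related quality of life questionnaire" among the tests before randomisation, and Section 8.2 names the instrument: "Health related quality of life (HRQOL) for the child and family will be determined using the validated Child Health Questionnaire". In Section 8.4, after the intervention period, "all children will be asked to return for a follow-up visit during which the following assessments will be made"; the list that follows includes the HRQOL questionnaire again.

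**The concern.** The baseline score of the same scale is usually among the best predictors of the follow-up score. Here it is collected and then left out of the comparison. The between-child variation that it would explain stays in the error term. With 36 to 50 children per arm that variation is large relative to any plausible effect, and a chance difference between the arms at baseline is carried into the 4-month difference.

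The trial is also meant to inform the size of a larger one. Section 9.0 asks for group summaries and tests, but for no between-arm difference with a confidence interval. A regression would supply that, together with the residual SD and the baseline/follow-up association that a future HRQOL sample-size calculation needs.

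**Working it through.** **Inputs.** From the documents: at least 36 evaluable children per group, with an aim of 50 (Section 3, number of subjects), and a 5% level, taken as two-sided. Not in the documents, so assumed: r between baseline and 4-month HRQOL of 0.3 to 0.7; an effect of 0.5 SD; the same instrument at both visits.

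**The plan's own figure.** None is given for HRQOL. The 36 per group belongs to the primary outcome and comes without an SD or dispersion, so it cannot be reproduced. Five against 3.33 visits as Poisson counts over one year gives 24 per group. A comparison of two means gives 36 only if the SD is taken as about 2.5. The document itself says the number is not a precise power calculation. I use 36 only as the number of children.

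**Variance of the arm difference**, relative to comparing 4-month scores alone:

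- 4-month scores alone: 1
- change scores: 2(1 − r)
- baseline-adjusted regression (large-sample): 1 − r²

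**Power.** Noncentral t with 70 df, two-sided 5%, noncentrality = 0.5 / √(1 − r²) × √(36/2). The detectable difference at 80% power is (1.96 + 0.842) × √(2/36) × √(1 − r²), in SD units. The equivalent sample size for an unadjusted test is 72 / (1 − r²).

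| | Unadjusted | r = 0.3 | r = 0.5 | r = 0.7 |
|---|---|---|---|---|
| Variance, adjusted | 1 | 0.91 | 0.75 | 0.51 |
| Variance, change score | – | 1.40 | 1.00 | 0.60 |
| Noncentrality | 2.12 | 2.22 | 2.45 | 2.97 |
| Power, 36 per arm | 55% | 59% | 68% | 83% |
| Detectable difference (SD) | 0.66 | 0.63 | 0.57 | 0.47 |
| Equivalent total n | 72 | 79 | 96 | 141 |

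A simulation with 20,000 replicates, which pays for estimating the slope, gives 55% unadjusted and 58%, 67% and 83% adjusted. Type I error is 5% for both tests. With 50 per arm (noncentrality using √(50/2), 98 df), power goes from 70% to 74%, 82% and 93%.

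**Chance imbalance.** The baseline difference between arms has SD √(2/36) = 0.24 SD units. It exceeds 0.25 SD in either direction in 2 × [1 − Φ(0.25/0.236)] = 29% of trials. In simulated trials where it exceeded +0.25 SD, the unadjusted estimate was off on average by 0.11, 0.18 and 0.26 SD at the three values of r, and the adjusted estimate by about 0. This is the precision loss seen from another side. The unadjusted variance is (2/n)[r² + (1 − r²)], and the r² part is the chance imbalance.

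**Price of adjustment.** With N children and q covariates, the finite-sample variance is inflated by about (N − 3)/(N − 3 − q).

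- HRQOL, N = 72, baseline only: 69/68 = 1.015. Adjustment loses only if r² < 1 − 68/69, that is, r below about 0.12.
- HRQOL, N = 72, baseline plus sex and age group, both taken as unprognostic and unbalanced: 69/66 = 1.045. The break-even r is √(1 − 66/69), about 0.21. Stratified randomisation tends to balance sex and age group, which lowers this cost.
- Full lung clearance index (LCI), at the 27% success rate in Section 8.2: about 0.27 × 36 ≈ 10 per arm, N = 20. With three covariates, 17/14 = 1.21 at r = 0 and 1.21 × 0.91 = 1.10 at r = 0.3. Here the full model can do worse than the plain test.

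**The case against.** The strongest reply is that Section 9.0 never names HRQOL and does not say whether the 4-month score or the change is tested. A reader might infer that a comparison of 4-month scores alone is prescribed. The text supports only this: all numerical data go to a two-sample test, and no use of baseline is stated. Neither reading removes the point, because in large samples the adjusted analysis is at least as precise as either. It is not so at every r in small samples, as the break-even figures show.

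A reader might also infer that the planned test is biased or has the wrong error rate. It is not and does not. Its confidence interval already allows for chance imbalance, so lost precision and imbalance should not be counted as two faults.

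The size of the gain rests on r, and the documents give reasons why r could be low. Inhaled steroids are stopped for 2 weeks before the baseline visit (Section 8.2), treatment is then started or stopped by arm (Section 6.1), and clinical phenotype may switch within 3 months (Section 1.1). At r = 0.3 the gain in power is only about 4 percentage points. That stands, and is why the range starts there.

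Three wider readings are not supported:

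- **Lung function and exhaled nitric oxide (FeNO)** are measured at both visits but are not listed outcomes, so they do not carry the point.
- **Admissions:** the eligibility history combines steroid courses with admissions (Section 3, type of subjects), so a separate prior admission count cannot be assumed to be on file as a covariate.
- **HRQOL as the only outcome reported by families:** unscheduled visits are also collected by weekly calls to families (Section 3).

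**Conclusion.** The point holds for HRQOL as a matter of efficiency. The planned analysis is valid but leaves out a baseline score that the trial collects anyway. Under the assumed r of 0.3 to 0.7, adjustment removes about 9% to 49% of the variance, and power for an assumed 0.5 SD effect at 36 per arm goes from 55% to between 59% and 83%. The absence of adjustment is certain from the text; the size of the gain is not, because the documents give neither r nor an HRQOL target. The primary outcome is untouched. The change is worth making for a listed secondary outcome, but the trial does not depend on it.

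**What to change.** In Section 9.0, before the data are analysed, state that HRQOL will be handled as follows:

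- Name the score or scores that form the outcome.
- Fit a linear regression of the 4-month score on arm, baseline score, sex and age group as used in randomisation. Report the adjusted mean difference with its 95% CI, using robust standard errors or a transformation if the scores are skewed.
- Keep children with a missing baseline score by mean imputation plus a missingness indicator, so that no child with a 4-month score is dropped.
- Report the two-sample test as a sensitivity analysis.

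The same model may be used for FeNO and LCI0.5 as exploratory measures, with baseline as the only covariate where few children have data. It should not be applied in full to LCI at the 27% success rate.

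The cost is a few sentences and a few degrees of freedom, with a slight loss of precision if r is near zero. No new visits, data or children are needed.

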## STUDY SUMMARY

**TITLE:** Use of pathological phenotype to determine optimal management for moderate to severe preschool wheeze

**SHORT TITLE:** Preschool wheeze: Inflammation/Infection Guided Management (PrIGMa)

**RATIONALE:** At least one-third of all children under 5 years suffer from wheezing and breathlessness, but despite the high incidence, there are few effective therapies. Current guidelines recommend the management of preschool wheezing should be determined by clinical phenotype. However, this is based predominantly on expert consensus with little evidence. The current guidelines have not been compared to other strategies. Current management does not take account of objective evidence of underlying inflammation or infection, however there is evidence to support that preschool wheezers have pathologically distinct phenotypes. This study will therefore determine the efficacy of treating preschool wheeze based on objective biomarkers of inflammation and presence of bacterial infection, and compare this to current clinical guidelines based management. This is a novel approach to managing preschool wheeze, which if effective, will have a significant impact on changing current clinical practice, and can be instituted within 5 years.

**AIMS:** To compare management of preschool wheeze using current clinical guidelines to management determined by eosinophilic inflammation in sputum or blood, and infection in sputum or oropharyngeal swabs

To determine numbers that would be needed to perform a large, multi-centre randomised trial comparing management according pathological phenotype to current clinical guidelines

**DESIGN:** Randomised, single blind, controlled trial comparing management of preschool wheeze based on inflammation and infection profile to current standard of care – the intervention will be over a 4 month period. This is a proof of concept study to determine feasibility of this approach and to obtain data to allow an assessment of numbers that would be needed for a larger randomised trial.

Subjects will be recruited from out-patient clinics and attend for a screening / research visit during which assessments of pathological phenotype (bacterial infection and inflammation) will be made from induced sputum and blood. Their clinical phenotype will be determined by the Consultant. Subsequently, patients will be randomised to one of two arms:

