**OUTCOME MEASURES:**

**Primary outcome** – number of unscheduled healthcare visits (UHCV) during the 4 month intervention period

**Secondary outcomes** – health related quality of life, number of hospital admissions, number of days of oral steroids during the 4 month intervention period, and up to 1 year later

**POPULATION:** Preschool children, aged 1-5 years attending out-patient clinic for recurrent wheezing

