#### **4.2 Inclusion criteria**

Age  $\geq$  1 years, <6 years  
Reported recurrent wheeze, needing at least 2 admissions +/- oral steroids in the last 12 months, at least one admission +/- oral steroids in the last 6 months

Past wheeze confirmed by a clinician

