## 5. RANDOMISATION AND ENROLMENT PROCEDURE

### 5.1 Randomisation practicalities

All randomisation and enrolment will occur during routine working hours – as all research visits will take place in the Biomedical Research Unit during the week between 9am and 5pm. Children will be recruited when they are clinically well, not during an acute attack.

We will use the Imperial INFORM database Unit to undertake randomisation

We wish to stratify randomisation according to sex and age, to achieve similar numbers of boys and girls in each group, and to have a similar average age for each group.

The age stratification will be as follows: >1-  $\leq$ 3 years and >3 -  $\leq$ 5 years

As wheezing in preschool children is a seasonal disorder (majority of symptoms and exacerbations occur between September – April each year), the baseline assessments and pre-randomisation visits will be arranged between late August – December each year, so that randomisation and intervention take place between September – January each year, to allow the 4 month intervention period to fall within the main season.

All patients will be given a study specific 24hrs emergency contact card immediately after being randomised. The card includes details of the study: Study title, patient trial number, CI/PI's contact details along with out of hours contact details in case of emergency.

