### 8.2 BASELINE ASSESSMENTS

At the clinic appointment parents of eligible children will be approached and will be verbally informed about the study and given a written information sheet. Parents' contact details will be taken and after a few days will be telephoned to ask whether they would like to take part in the study. Once parents have agreed, they will be invited for a research visit for baseline assessments prior to randomisation.

As wheezing in preschool children is a seasonal disorder (main symptoms between September – April each year), the baseline assessments and pre-randomisation visits will be arranged between late August – December each year, so that randomisation and intervention take place between September – January each year, to allow the 4 month intervention period to fall in the main season.

All baseline assessments will be made providing the child has not had any acute wheezing episodes within the last 2 weeks. Also, with their Consultant's permission, parents will be asked to stop administering any regular inhaled steroids (if they have been taking them) for 2 weeks prior to the research visit.

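### Section 9 commits to no rate ratio or interval for the primary visit count, and the one model it names for that count, a Poisson regression, has no allowance for overdispersion

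*Combined protocol and SAP*

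**What the plan says.** The primary outcome in the Study Summary is the "number of unscheduled healthcare visits (UHCV) during the 4 month intervention period", and Section 3.1 agrees. It is a count per child.

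Section 9.0 is the whole analysis plan, apart from the intention-to-treat statement in Section 4.4. It handles numerical data by a general rule: test for normality, then use a t test or, failing normality, "For the data that are not normally distributed the median (IQR) will be presented and comparisons between groups done using the Mann-Whitney test". For the primary endpoint it adds: "Poisson regression will be done to determine the factors that affect the primary endpoint, the number of unplanned hospital visits".

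Section 9.0 does not label either method as the primary treatment comparison. It lists no model terms, offset, overdispersion allowance, rate ratio or confidence interval. It also names the endpoint differently from the Study Summary and Section 3.1 (hospital visits rather than healthcare visits).

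Three other places bear on the choice:
- Section 5.1: "We wish to stratify randomisation according to sex and age".
- Section 4.4: data collected before a withdrawal are kept if the family agrees, so some children will contribute less than 4 months.
- Study Summary, Design: one purpose is to "obtain data to allow an assessment of numbers that would be needed for a larger randomised trial". Section 8.6 repeats this aim.

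**The concern.** Two methods apply to the same primary count, and they do different things.

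Mann-Whitney tests for a difference but does not estimate a rate ratio, and it takes no account of the two factors used to stratify randomisation. A later trial with a count endpoint is sized from a control rate, a rate ratio and a dispersion, and Section 9.0 commits to reporting none of them.

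The Poisson regression could supply a rate ratio. In its plain form it assumes that the variance equals the mean. Children who wheeze repeatedly may differ in their underlying visit rate, which makes the variance larger. Plain Poisson standard errors are then too small and p-values overstate the evidence, for arm or for any other factor examined.

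With no primary comparison named, the choice between the methods could also settle whether the result is called significant.

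**Working it through.** **Inputs from the documents.** Control rate: "approximately five healthcare attendances occur per child per year" (Number of subjects). Target effect: a one-third reduction. Minimum size: 36 per group. Significance level: 5%, taken as two-sided. The 36 per group cannot be reproduced, because no SD, dispersion or formula is given. It is used here only as the trial size.

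**Assumptions.**
- Gamma-Poisson dispersion k = 0, 0.25, 0.5 or 1, where variance = m(1 + km) for mean m.
- A rate constant over the year; alternatively a higher in-season mean of 2.5 visits per 4 months, since Section 8.2 times the visits "to allow the 4 month intervention period to fall in the main season".

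**Step 1. Means.** Control: 5 × 4/12 = 1.67 visits per 4 months. With a one-third reduction: 1.67 × 2/3 = 1.11.

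**Step 2. Which test the general rule selects.** The normality test is not specified. With Shapiro-Wilk, normality is rejected in at least one arm in essentially every simulated trial at mean 1.67, and in 98-100% at mean 2.5. The rule therefore leads to Mann-Whitney.

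**Step 3. Plain Poisson when arms do not differ.** The true standard error exceeds the Poisson one by √(1 + km), so the actual type I error is 2[1 − Φ(1.96/√(1 + km))].

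| k | 0 | 0.25 | 0.5 | 1 |
|---|---|---|---|---|
| Variance/mean at 1.67 | 1.00 | 1.42 | 1.83 | 2.67 |
| SE factor at 1.67 | 1.00 | 1.19 | 1.35 | 1.63 |
| Type I error by formula, mean 1.67 | 5.0% | 10.0% | 14.8% | 23.0% |
| Type I error by simulation, 36 per arm, mean 1.67 | 4.9% | 9.9% | 14.3% | 22.7% |
| Type I error by formula, mean 2.5 | 5.0% | 12.4% | 19.1% | 29.5% |

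At mean 1.67 in the same simulation, Pearson-scaled (quasi-Poisson) standard errors gave 4.9 / 4.9 / 4.9 / 5.2%. In a run with arm, sex and age in the model, Mann-Whitney on the same data gave 4.6-4.8%.

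**Step 4. Disagreement on significance at 1.67 v 1.11, 36 per arm.**

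| k | 0 | 0.25 | 0.5 | 1 |
|---|---|---|---|---|
| Plain Poisson v Mann-Whitney | about 10% | 17% | 24% | 32% |
| Quasi-Poisson v Mann-Whitney | about 9% | 10-12% | 12% | 13% |
| Excess (percentage points) | 1 | 5-7 | 12 | 19 |

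The second row is ordinary disagreement between two valid tests. Only the excess comes from the missing allowance.

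**Step 5. Width of an honest interval.** With quasi-Poisson, the 95% CI for the rate ratio is the estimate divided and multiplied by about 1.51 / 1.62 / 1.71 / 1.88. An estimate of 0.67 would have limits of about 0.44-1.01, 0.41-1.08, 0.39-1.14 and 0.35-1.25. Relative to k = 0, the widening on the log scale is ln 1.62/ln 1.51 = 1.17, ln 1.71/ln 1.51 = 1.30 and ln 1.88/ln 1.51 = 1.53.

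**The case against.** The strongest reply is that the plan does imply an arm comparison. Section 9.0 attaches comparisons between groups to the t test or Mann-Whitney, and gives the Poisson model a different job. On that reading the test is sound: it holds 5%, and its power is only 1 to 5 points below quasi-Poisson (47 v 48, 35 v 38, 28 v 32 and 20 v 25% at k = 0, 0.25, 0.5 and 1). This stands. A reader might infer that the trial's primary test is invalid, or that its false-positive rate is up to 23%. The documents do not support that. The inflation needs both a plain Poisson model used for the arm effect and overdispersed counts. No dispersion is given, and at k = 0 there is no inflation. Silence on overdispersion is also not a decision to ignore it.

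A reader might also take the whole 10-32% disagreement as the cost of the gap; Step 4 shows it is not. Nor is it safe to say that the medians would hide a real effect. The population medians are 1 v 1 at means 1.67 and 1.11, but sample medians in trials of 36 per arm are 1 v 1 in only about 43-59% of cases.

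Finally, Sections 3 and 8.6 present this as a proof-of-concept study, and arm rates, rate ratio and dispersion can all be computed later from the per-child counts. That lowers the stakes. It does not answer the point that the plan commits to reporting none of them, although sizing the next trial is a stated aim.

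**Conclusion.** The point holds in limited form and should be fixed. The arm comparison, read literally, is valid but unlabelled. It ignores the randomisation strata and gives no rate ratio or interval. The only model named for the primary endpoint has no stated protection against overdispersion.

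If that model is used as plain Poisson, type I error for the arm effect is about 5 / 10 / 14 / 23% at k = 0 / 0.25 / 0.5 / 1 with mean 1.67, and about 5 / 12 / 19 / 29% with mean 2.5. Pearson scaling brings it back to about 5%. The excess disagreement with Mann-Whitney is about 1 to 19 points over the same range of k at mean 1.67.

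The dispersion values and the 2.5 mean are assumptions. The gaps in Section 9.0 do not depend on them; the size of the inflation does.

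**What to change.** In Section 9.0:

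- Name one primary arm comparison: a log-link count regression of the 4-month unscheduled healthcare visit count with overdispersion-scaled standard errors (for example quasi-Poisson), terms for arm, sex and age, and log(days observed) as offset. The offset is needed because Section 4.4 keeps data up to withdrawal. Age in years is convenient, since the Section 5.1 bands stop at 5 while Section 4.2 admits children up to 6.
- Report the rate in each arm, the rate ratio with 95% CI, and the dispersion. State whether the dispersion is the Pearson scale or the gamma-Poisson parameter, because a later sample-size calculation must know which.
- Keep Mann-Whitney as a sensitivity analysis, with no normality test deciding the primary method.
- Label the factors model exploratory and apply the same scaling to it.
- Use the endpoint name of the Study Summary and Section 3.1.

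The cost is wording and a few lines of code. No new data are needed: sex and age are known at randomisation, and visits are recorded in the weekly calls. The downsides are intervals wider than plain Poisson by a factor of about 1.17 / 1.30 / 1.53 at a one-third reduction with k = 0.25 / 0.5 / 1, and three model terms in 72-100 children. The offset does not cure informative withdrawal.

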## **3. STUDY DESIGN**

This is a single blind, randomised, controlled trial comparing management of moderate to severe preschool wheeze according to current clinical guidelines to management determined by inflammation and infection profile (pathological phenotype).

**Study duration:** The intervention phase of the study will last for 4 months, with follow-up immediately after the intervention period and 6 monthly thereafter until the end of the trial. The minimum follow-up is at the end of the 4 month intervention period, maximum follow-up will be for 3 years. During the 4 month intervention period, families will be contacted weekly by phone call for an update on unscheduled healthcare visits and symptoms.

**Type of subjects to be recruited:** All subjects will be aged between 1 and 5 years old. All subjects will have moderate to severe preschool wheeze, defined as  $\geq 2$  oral steroid bursts OR hospital admissions for acute wheeze in the last 12 months, with at least one oral steroid burst OR hospital admission in the last 6 months.

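### The between-arm comparison of visit counts prespecifies no adjustment for baseline attack history, a cheap and probably modest gain in precision left untaken

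*Combined protocol and SAP*

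**What the plan says.** The primary outcome (section 3.1) is the "number of unscheduled healthcare visits in the 4 month intervention period".

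Section 9.0 is the whole analysis plan. Numerical data are tested for normality and then compared between groups by a two-sample t test or a Mann-Whitney test. One further sentence concerns the primary endpoint: "Poisson regression will be done to determine the factors that affect the primary endpoint". It lists no factors, does not say whether arm is in the model, and does not say which analysis is primary.

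Attack history appears as an entry threshold. Section 3 requires at least two events in 12 months, "with at least one oral steroid burst OR hospital admission in the last 6 months". The baseline questionnaire in section 8.2 covers severity and medication history but does not name a count of attacks.

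Section 5.1 stratifies randomisation by sex and age only. It addresses season through scheduling: "As wheezing in preschool children is a seasonal disorder", randomisation is confined to September to January.

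**The concern.** A child's recent attack rate is a natural candidate predictor of visits over the next four months, and the eligibility check already requires staff to look at it. If it predicts the outcome, an analysis that ignores it leaves explainable between-child variation in the error term, and the rate ratio is estimated less precisely than the same children would allow. With a minimum of 36 per arm there is little precision to spare.

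The open Poisson sentence adds a second weakness. Because its terms are not fixed, covariates could be chosen after the data are seen, and it is unclear which result would be reported as the arm comparison. The trial is also meant to inform the size of a larger one, and the dispersion left after adjusting for history would be a useful input to that calculation.

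**Working it through.** **Inputs from section 3 (Number of subjects).** The control rate is "approximately five healthcare attendances occur per child per year". The aim is to "reduce the proportion of healthcare contacts by at least one-third per year", taken here as a rate ratio of 2/3, "with 80% power, and accepting statistical significance at the 5% level" (two-sided assumed). The stated size is: "we require a minimum of 36 evaluable patients with moderate wheeze per group".

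Spread evenly, the 4-month control mean is m1 = 5 × 4/12 = 1.67, and the treated mean is m2 = 1.67 × 2/3 = 1.11.

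**The plan's own figure.** With between-child dispersion k, n per arm = (1.960 + 0.842)² × (1/m1 + 1/m2 + 2k) / (ln 1.5)². Here (1.960 + 0.842)² = 7.85 and (ln 1.5)² = 0.1644.
- 12-month count, k = 0: 7.85 × (0.2 + 0.3) / 0.1644 = 23.9, so 24 per arm.
- 4-month count, k = 0: 7.85 × (0.6 + 0.9) / 0.1644 = 71.6, so 72 per arm.

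Neither gives 36. An annual SD of about 2.52 would, but no SD is stated and the plan disclaims a precise calculation. So 36 is not derivable from the documents; it is not shown to be wrong.

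**Starting precision at 36 per arm, 4-month count.** SE = √[(1/m1 + 1/m2 + 2k)/36] and power = Φ(0.405/SE − 1.96).
- k = 0: SE = √(1.5/36) = 0.204, power 0.51.
- k = 0.5: SE = √(2.5/36) = 0.264, power 0.34.
- k = 1: SE = √(3.5/36) = 0.312, power 0.25 to 0.26.

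**General rule for adjustment.** If covariates explain a share R² of the outcome variance, the variance is multiplied by 1 − R², and 36 per arm acts like 36/(1 − R²). The R² values are assumptions.

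| R² | SE multiplied by | 36 per arm acts like |
|---|---|---|
| 0.05 | 0.975 | 37.9 |
| 0.10 | 0.949 | 40.0 |
| 0.20 | 0.894 | 45.0 |
| 0.30 | 0.837 | 51.4 |

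**Simulation at 36 per arm.** All settings are assumptions: control mean 1.67, gamma frailty (a child's underlying propensity to attacks) with variance 0.3 to 1.0, prior-year mean 2 to 4 with at least 2 events required, and a rate that declines over start months. Quasi-Poisson with arm alone was compared with arm plus log prior count plus month.
- Same frailty drives history and outcome: variance factor about 0.67 to 0.97, equivalent to 36/0.97 = 37 up to 36/0.67 = 54 per arm. Power rises about 2 to 10 points.
- Latent correlation 0.5: variance factor about 0.93 to 1.0, equivalent to 36 up to 36/0.93 = 39 per arm. Power rises about 0 to 3 points.

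A separate simulation used Poisson regression with robust standard errors and shared frailty. The SD of the log rate ratio fell 3–8% at k = 0.25–0.5 (variance factor 0.97² = 0.94 to 0.92² = 0.85) and 17–19% at k = 1 (0.83² = 0.69 to 0.81² = 0.66). At the 50-per-arm target with k = 1 and no seasonal effect, power went from 0.445 to 0.563, a gain of 11.8 points, so the upper end of the power range is approximate.

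**Month of randomisation.** Four months from a September to December start end by April; only January starts run past it. With a flat in-season rate and 67–100% of visits falling in September to April, start date explains at most 0.9% of the variance. An assumed two-fold decline from September to January starts gives R² of 0.02–0.06. In simulation, month alone changed the SD by −4% to +1%.

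**The case against.** Four objections deserve weight.

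**The regression could include both variables.** The Poisson sentence leaves its factors open. A reader might infer that the plan excludes attack history and month from every analysis of visits. The text does not support that; it supports only that neither is prespecified and that the named two-group tests cannot use them.

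**The count may not be recorded, and has no single definition.** A reader might assume the trial already holds a numeric prior-year count. The documents show only a threshold. Its wording also differs: steroid courses or admissions in the Study Summary and section 3, steroid courses alone in section 2, and admissions with or without steroids in section 4.2. This objection stands, and it shapes the fix.

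**Neither variable is shown to be a strong predictor.** The documents give no correlation with visits. History counts steroid courses or admissions, whereas the outcome is any unscheduled visit, so a perfect latent correlation is a best case. One set of runs at correlation 0.5 gave variance factors of 0.91 to 1.05 and power changes of about −1 to +4 points, so a small loss is possible. Gains of around 22 points appear only under more favourable assumptions, such as a control mean of 2.5 with strong shared heterogeneity, and should not be read as expected.

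**Unadjusted analysis of a randomised trial is valid.** Chance imbalance in history or start month is already reflected in the standard error and is not bias. The trial is also described as proof of concept. Both points stand and limit the concern to efficiency and prespecification.

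**Conclusion.** The concern holds as a precision and prespecification point. The named arm comparisons are unadjusted, and the only regression fixes neither arm nor covariates, so attack history has no prespecified place in the primary comparison.

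The likely benefit runs from almost nothing to moderate. It depends on how much children differ in underlying rate and on how closely past attacks track future visits, and the documents give neither. Nearly all of any gain comes from history. Month adds almost nothing, because the recruitment window removes much of the seasonal contrast, and nothing in the documents supports a linear trend across start months.

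A reader might infer that adjustment would bring the trial to its nominal 80% power, or that the unadjusted result would be biased. Neither follows: starting power for the 4-month count at 36 per arm is about 0.51 with no over-dispersion and lower with it, and a gain of 10 points would not close that gap.

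**What to change.** - In section 9.0, name one primary model for the 4-month visit count that allows over-dispersion (quasi-Poisson, Poisson with robust standard errors, or negative binomial), containing treatment arm and the log of the number of oral-steroid courses or admissions in the 12 months before entry. State that the arm coefficient is the primary comparison.
- Define that count once, including how an admission treated with oral steroids is counted, and reconcile the Study Summary, section 2, section 3 and section 4.2.
- Record the count as a number on the baseline CRF, not only that the threshold was met.
- Treat month of randomisation as optional. If it is included, fix its form in advance and do not assume linearity.
- Use the same outcome term throughout: section 9.0 refers to hospital visits, whereas section 3.1 covers healthcare visits generally.

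The cost is one or two model terms and one numeric CRF field. No extra visit, sample or child is needed.
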